8.2.1. Headache Pain Freedom at 2 Hours Postdose During DB2 Period

The proportion of subjects who are free from headache pain at 2 hours after the first dose of study medication taken for a migraine attack with headache pain of any level during the DB2 treatment period will be summarized by treatment group for the FAS2 (ie, headache pain rating of mild [Grade 1], moderate [Grade 2] or severe [Grade 3] predose reduced to none [Grade 0] at 2 hours postdose). The 95% exact CIs for those proportions, the odds ratio for response, and corresponding p-value from Fisher's exact test will be computed for the comparison between treatment groups.

8.2.2. Headache Pain Freedom Postdose

The proportion of subjects who are free from headache pain at 10, 15, 20, 30, 60, and 90 minutes after the first dose of study medication during each DB treatment period will be summarized by treatment group for the FAS1 and FAS2. The corresponding p-values from Fisher's exact test will be computed for the comparison between treatment groups.

8.2.3. Headache Pain Relief Postdose

The proportion of subjects who have pain relief at 10, 15, 20, 30, 60, 90, and 120 minutes after the first dose of study medication will be summarized by treatment group and time point for the FAS1 and FAS2. Headache pain relief is defined for DB1 as a reduction from moderate or severe pain prior to dosing to mild or none postdose, and for DB2 as moderate or severe pain before dosing reduced to mild or none postdose, or mild pain before dosing reduced to none postdose. The corresponding p-values from Fisher's exact test will be computed for the comparison between treatment groups. Subjects who report a headache pre-dose and rate the headache pain level at the particular postdose time point will be analyzed.

8.2.4. Absence of MBS Postdose

The proportion of subjects with their MBS among nausea, photophobia and phonophobia absent at 10, 15, 20, 30, 60, 90, and 120 minutes after the first dose of study medication taken for a migraine attack during each DB treatment period will be summarized by treatment group and time point for the FAS1 and FAS2. The corresponding p-values from Fisher's exact test will be computed for the comparison between treatment groups. Subjects who report a MBS pre-dose and report the status of the MBS at the particular postdose time point will be analyzed.

8.2.5. Freedom from Nausea, Photophobia, and Phonophobia Postdose

The proportion of subjects who are free from nausea, photophobia, and phonophobia at 10, 15, 20, 30, 60, 90, 120 minutes and 24 hours after the first dose of study medication taken for a migraine attack during each DB treatment period will be summarized by symptom, treatment group, and time point for the FAS1 and FAS2. The corresponding p-values from Fisher's exact test will be computed for the comparison between treatment groups. Subjects who report a symptom pre-dose and report the status of the symptom at the particular postdose time point will be analyzed.

8.2.6. Time to Pain Relief and Pain Freedom Postdose

The following two secondary efficacy endpoints are captured in the subject eDiary separately from the scheduled time points, and are self-initiated based on the actual time of a subject's perception of pain relief and pain freedom (if they occur) within the first 2 hours postdose. Descriptive statistics for the two endpoints will be provided by

treatment group for the FAS1 and FAS2. Additionally, the two endpoints will be summarized and graphically presented by treatment group for the FAS1 and FAS2 using Kaplan-Meier survival estimation. Comparisons between treatment groups will be performed using the log-rank test.

8.2.6.1. Time to Meaningful Headache Pain Relief Postdose

Time to meaningful headache pain relief is defined as the time in minutes from the time a subject takes study medication until the time a subject indicates meaningful pain relief in the eDiary within 2 hours postdose. The time to meaningful headache pain relief postdose will be summarized and analyzed using Kaplan-Meier survival estimation for the FAS1 and FAS2. The corresponding p-values from a log-rank test will be computed for the comparison between treatment groups.

8.2.6.2. Time to Headache Pain Freedom Postdose

Time to headache pain freedom is defined as the time in minutes from the time a subject takes study medication until the time a subject indicates pain freedom in the eDiary within 2 hours postdose. The time to headache pain freedom postdose will be summarized and analyzed using Kaplan-Meier survival estimation for the FAS1 and FAS2. The corresponding p-values from a log-rank test will be computed for the comparison between treatment groups.

8.2.8. Sustained Headache Pain Freedom at 24 Hours

The proportion of subjects who have sustained headache pain freedom at 24 hours (from 2 to 24 hours) after the first dose of study medication taken for a migraine attack during each DB treatment period will be summarized by treatment group for the FAS1 and FAS2. Sustained headache pain freedom at 24 hours is defined as pain free at 2 hours postdose, with no use of rescue medication or additional study medication and no recurrence of headache pain within 2 to 24 hours postdose. The corresponding p-values from Fisher's exact test will be computed for the comparison between treatment groups.

8.2.9. Change in Functional Disability Score Postdose

The values of the functional disability scale are: 0 = no disability, able to function normally; 1 = performance of daily activities mildly impaired, can still do everything but with difficulty; 2 = performance of daily activities moderately impaired, unable to do some things; 3 = performance of daily activities severely impaired, cannot do all or most things, bed rest may be necessary.

The change in functional disability score from baseline to 2 hours and 24 hours after the first dose of study medication taken for a migraine attack during each DB treatment period will be summarized by treatment group for the FAS1 and FAS2. The corresponding p-values from the Wilcoxon signed-rank test will be computed for the comparison between treatment groups.

The following levels of change from baseline in functional disability score will be compared between DFN-02 and placebo in each DB period: 3 point change, 2 point change, 1 point change, 0 point change, -1 point change, -2 point change, and -3 point change. The proportion of subjects with those levels of change from baseline during each DB treatment period will be summarized by treatment group and time point for the FAS1 and FAS2. The corresponding p-values from Fisher's exact test will be computed for the comparison between treatment groups for each category.

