10.2.1.4 End of DB2 Period (Visit 4); End of Treatment (or Early Termination)

- Confirm the following:
 - Visit is within 2 to 7 days of treatment of a migraine attack with study medication dispensed at V3 (or ET, if applicable)
 - Treatment should be completed within 10 weeks from V2
- Review/collection of AEs
- Physical examination (if warranted)
- Weight of patient
- Vital signs measurement (sitting SBP/DBP, pulse rate, and body temperature); record menses
- Urine pregnancy test for women of childbearing potential
- Blood draw for hematology and clinical chemistry, including HbA1c
- Urine collection for urinalysis
- Urine drug test and ethanol screen
- 12-lead ECG
- Concomitant medication review, including from eDiary entries
- Confirm patient compliance and study medication accountability
- Review, confirm, and ensure proper recording of eDiary entries by patient
- Collection of eDiary; empty study medication containers, and all unused study medication

CONFIDENTIAL

10.2.1.4.1 eDiary Assessments

Patients will be provided with an eDiary at screening (V1) to collect at least 1 migraine episode data and, if randomized (V2), to continue to collect migraine date and time (for migraine attacks treated with study medication) and any non-study medication used to treat migraine in the study. At V2 and V3, patients will be re-instructed on the eDiary usage to ensure real-time entry of predose and postdose recordings. (Predose migraine assessments will be allowed to be recorded retrospectively in the event a patient did not follow the instructions.) All patients should be instructed to return the eDiary to the study site.

At baseline (V2), patients will complete the PPMQ-R questionnaire in the eDiary; record the migraine pain start and end (date and time) when they get the migraine; record the baseline pain level; record the functional disability scale; and record presence of symptoms and MBS (among nausea, photophobia, and phonophobia) just before taking the study medication.

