11.6.2 Secondary Efficacy Analysis

The secondary endpoints for proportion of patients who are free from headache pain, for proportion of patients with their MBS absent, for proportion of patients who are free from nausea, photophobia, and phonophobia, for proportion of patients who have pain relief, for proportion of patients who have sustained pain freedom, and for proportion of patients who use a second dose of the study medication or rescue medication, will be analyzed using Fisher's exact test similarly to the described analysis for the primary endpoint.

The secondary endpoints for time to meaningful pain relief and time to pain freedom will be analyzed using Kaplan-Meier product-limit method.

The secondary endpoints for the change in functional disability score at 2 hours and 24 hours after the first dose of study medication will be analyzed using Wilcoxon signed-rank test. The secondary endpoints for treatment satisfaction at 2 hours postdose as measured on the 7-point scale, and at 24 hours postdose as measured by the PPMQ-R, will be analyzed using the Wilcoxon rank-sum test.

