11.8 Determination of Sample Size

One hundred patients will be randomized for the DB1 treatment period. Patients who discontinue participation without completing the study protocol will not be replaced.

The primary endpoint is the comparison of the proportion of patients who are pain-free at 2 hours after the first dose of study medication. It is assumed that 15% of placebo and 42% of DFN-02 (treated) patients will be pain-free at 2 hours. A sample size of 50 patients in each DB1 dosing arm will provide 81% power to detect this assumed difference between placebo and DFN-02 at a 5% (2-sided) level of significance.

12 Quality Assurance and Quality Control

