3.6. DETERMINATION OF SAMPLE SIZE

Approximately 100 subjects will be randomized for the DB1 treatment period. Subjects who discontinue participation without completing the study protocol will not be replaced.

The primary endpoint is the comparison of the proportion of subjects who are pain-free at 2 hours after the first dose of study medication. It is assumed that 15% of placebo and 42% of DFN-02 10 mg (treated) subjects will be pain-free at 2 hours. A sample size of 50 subjects in each DB1 dosing arm will provide 86% power to detect this assumed difference between placebo and DFN-02 10 mg at a 5% (2-sided) level of significance.

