3.7. TREATMENT ASSIGNMENT & BLINDING

The DFN-02-CD-012 study is a randomized, 2 DB treatment period, placebo-controlled study. Eligible subjects will be randomized in a 1:1 ratio in both DB periods to receive either DFN-02 10 mg or a matching placebo. The randomization schemes for both DB periods will be generated by the biostatistics group of INC Research. The interactive web response system (IWRS) will assign the appropriate study kit to each subject for each DB treatment period. If a subject discontinues from the study after randomization, the subject identification (ID) number and randomization number will not be reused, and the subject will not be allowed to re-enter the study.

All randomization data will be kept strictly confidential and accessible only to authorized personnel until the time of unblinding after database lock at the end of the study. Blinding is critical to the integrity of this clinical study; however, in the event of a medical emergency for an individual subject, in which knowledge of the treatment assignment is critical to the subject's management, the blind for the subject may be broken by the Investigator (or designee) by contacting IWRS. Before unblinding, the Investigator (or designee) should have determined that the treatment information is necessary to decide the subject's immediate management, and must make every effort to contact the Medical Monitor prior to unblinding. In many cases, especially if the emergency is clearly not related to study treatment, the problem may be properly managed without unblinding by assuming that the subject is receiving active treatment. In cases of accidental unblinding or when the Medical Monitor cannot be contacted prior to unblinding, the Medical Monitor should be contacted as soon as possible after the breaking of the blind and every attempt to preserve the blind for all other study staff should be made.

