6. GENERAL ASPECTS FOR STATISTICAL ANALYSIS

6.1. GENERAL METHODS

6.1.1. Summary Statistics

In general, descriptive statistical methods will be used to summarize the data from this study. With appropriate sample sizes, hypothesis testing can be performed for the primary and secondary efficacy endpoints.

The term "treatment group" refers to the applied treatment regimen during DB1 or DB2 (DFN-02 10 mg or placebo). All data collected during the study will be included in subject data listings. All subjects entered into the database will be included in subject data listings. Unless otherwise noted, the data will be sorted first by treatment group, subject number, and then by date within each subject number.

Unless stated otherwise, the term "descriptive statistics" refers to number of subjects (n), mean, median, standard deviation, minimum, and maximum for continuous data and frequencies and percentages for categorical data.

All categorical/qualitative data will be presented using absolute frequency counts and percentages. The total number of subjects in the treatment group overall (N) in the specified population will be used as the denominator for percentage calculations, unless stated otherwise in the table shell. All percentages will be presented in parentheses with 1 decimal point, unless otherwise specified. Percentages equal to 100 will be presented as 100% and percentages will not be presented for zero frequencies.

Unless specified otherwise, all statistical testing and confidence intervals (CIs) will be 2-sided and will be performed using a significance (alpha) level of 0.05.

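### SAP 8.2.9 compares raw change in functional disability between arms without adjusting for the predose score, which gives up precision even after its signed-rank test is corrected

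*SAP*

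**What the plan says.** SAP 8.2.9 defines a four-level disability scale (0 to 3). It analyses "The change in functional disability score from baseline to 2 hours and 24 hours after the first dose of study medication" by treatment group in FAS1 and FAS2, with p-values for the between-group comparison from the Wilcoxon signed-rank test. It adds a Fisher's exact test for each level of change, from +3 to -3. Protocol 11.6.2 assigns the signed-rank test to "The secondary endpoints for the change in functional disability score at 2 hours and 24 hours" as well. Neither section, nor SAP 8.2 or SAP section 11, names a covariate, stratum or model that uses the predose score.

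That score is collected. Protocol 10.2.1.4.1 has patients "record the baseline pain level; record the functional disability scale" just before taking study medication. The eDiary tables (Protocol Table 10-2, SAP Table 2) mark functional disability at predose, 2 h and 24 h. SAP 6.2.1 defines baseline separately for each DB period.

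The only sample-size reasoning concerns 2-hour pain freedom. No effect size, SD, correlation or power is given for disability. The general testing rule is that "all statistical testing and confidence intervals (CIs) will be 2-sided and will be performed using a significance (alpha) level of 0.05".

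**The concern.** A patient who starts at 1 can improve by at most 1 point, and one who starts at 3 can improve by 3. Raw change therefore carries the variability of the predose score, and chance imbalance in predose disability passes directly into the comparison. No stratification factor for randomisation is described, so such imbalance is possible with about 100 patients.

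This is distinct from the choice of Wilcoxon test. Changing signed-rank to rank-sum would make the comparison valid, but it would still ignore a baseline value that is already in the database. What is at stake is precision: a real benefit on disability is more likely to be missed than the data require.

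**Working it through.** **1. The plan's own power figure.** The inputs are for pain freedom: "It is assumed that 15% of placebo and 42% of DFN-02 10 mg (treated) subjects will be pain-free at 2 hours", 50 per arm, 5% two-sided. The SAP states "A sample size of 50 subjects in each DB1 dosing arm will provide 86% power to detect this assumed difference" and the Protocol states "A sample size of 50 patients in each DB1 dosing arm will provide 81% power to detect this assumed difference".

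Pooled normal approximation: mean rate 0.285; null SE = √(2 × 0.285 × 0.715 / 50) = 0.0903; alternative SE = √((0.15 × 0.85 + 0.42 × 0.58) / 50) = 0.0862. Then z = (0.27 - 1.96 × 0.0903) / 0.0862 = 1.08, which gives 86.0% and matches the SAP. Exact Fisher gives 81.7%, in line with the Protocol. Neither figure says anything about disability.

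**2. The named test.** A signed-rank test asks whether change differs from zero in one sample. In a simulated single arm of 50 with placebo-type improvement and no treatment effect, it rejected in about 98% of runs. It has no meaningful between-arm power, so the comparator below is the rank-sum test on change, the natural valid replacement.

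**3. Normal-theory direction.** Let k = predose SD / postdose SD and ρ = their correlation. Adjusted variance / change-score variance = (1 - ρ²) / (1 + k² - 2ρk). The reduction is therefore (k - ρ)² / (1 + k² - 2ρk), which is never negative and is zero when k = ρ. If the change-score analysis has 80% power:
- ρ 0.5, k 1.0: reduction 0.25 / 1.00 = 25%; power becomes 90%.
- ρ 0.3, k 0.8: reduction 0.25 / 1.16 = 22%; power becomes 89%.
- ρ 0.5, k 0.6: reduction 0.01 / 0.76 = 1%; power becomes 80.5%.

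**4. Simulation on the 0-3 scale.** All inputs are assumed except 50 per arm and two-sided 5%. A latent bivariate normal was cut to predose scores 0-3 of 5/25/45/25% (wide) or 2/18/60/20% (narrow) and placebo 2-h scores of 20/35/30/15%, with a latent shift of 0.6 SD and 2,500 trials per setting. Power in %, gain over rank-sum in points:

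| Predose spread | Latent ρ | Rank-sum on change | Van Elteren by predose score | ANCOVA | Gain, van Elteren | Gain, ANCOVA |
|---|---|---|---|---|---|---|
| Wide | 0.2 | 59.5 | 76.8 | 78.7 | 17.3 | 19.2 |
| Wide | 0.3 | 66.5 | 80.1 | 81.6 | 13.6 | 15.1 |
| Wide | 0.5 | 77.2 | 85.2 | 85.9 | 8.0 | 8.7 |
| Wide | 0.7 | 88.6 | 92.1 | 92.5 | 3.5 | 3.9 |
| Narrow | 0.2 | 69.4 | 78.8 | 81.1 | 9.4 | 11.7 |
| Narrow | 0.3 | 72.3 | 79.6 | 82.0 | 7.3 | 9.7 |
| Narrow | 0.5 | 81.3 | 83.9 | 85.2 | 2.6 | 3.9 |
| Narrow | 0.7 | 90.7 | 91.6 | 91.8 | 0.9 | 1.1 |

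With no effect, all three methods rejected in about 4% to 6% of trials. The Monte Carlo standard error of one power figure is about √(0.75 × 0.25 / 2500) = 0.9 points. A repeat with 10,000 trials per setting gave van Elteren gains of 0.8 to 16.9 points. For both adjusted methods together it gave 3.4 to 15.7 points at ρ 0.3 to 0.5, and 0.8 to 4.3 points at ρ 0.7.

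**The case against.** The strongest reply is that nothing here is invalid. Change in disability is the prespecified endpoint. Because "Eligible subjects will be randomized in a 1:1 ratio in both DB periods", an unadjusted between-arm comparison of change by a proper two-sample test is unbiased, and chance imbalance is already covered by its type I error. This is one of many unpowered secondary endpoints in a Phase 2 trial sized on pain freedom. All of that stands, and it limits the point to efficiency.

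Several stronger readings are tempting, and the documents do not support them:
- **A fixed loss, such as 3 to 15 points, in the planned analysis.** The signed-rank test has no valid between-arm power to lose, and every input that sets the size is an assumption.
- **The same gain at 24 h and in DB2.** Only a 2-h comparison was simulated. The 24-h score can follow a second dose or rescue medication. DB2 attacks are treated at any pain level, so a wider predose spread is plausible, but no DB2 distribution or FAS2 size is given.
- **The trial's only function endpoint.** The PPMQ-R has a four-item function subscale (SAP 8.2.12). It measures satisfaction, but it is also tested between arms.
- **A predose score always entered in real time.** Protocol 10.2.1.2 and 10.2.1.4.1 allow retrospective entry. This affects raw change equally.

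Fifty per arm is also an upper limit for the analysed number. Dropouts are not replaced, FAS1 requires a treated attack and a postdose assessment, and SAP 8.2 excludes patients with an early second dose or rescue. Smaller numbers lower power for every method and do not remove the reason to adjust.

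**Conclusion.** The point holds as a modest improvement in efficiency. SAP 8.2.9 leaves the predose score out of the between-arm comparison, and correcting the signed-rank test alone would not put it back.

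Under the stated assumptions (latent correlation 0.2 to 0.7, latent shift 0.6 SD, at most 50 per arm, 2 h), the stratified rank test adds about 1 to 17 points of power over a rank-sum test on raw change. Taking both adjusted methods, the gain is about 3 to 16 points at correlations of 0.3 to 0.5 and about 1 to 4 points at 0.7. ANCOVA reaches about 19 points at a correlation of 0.2 with a wide predose spread. These are illustrations, because the plan supplies none of the inputs that decide where in the range the trial falls. Adjustment had the higher power in all eight settings.

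In this section the signed-rank test is the larger defect. The missing adjustment is desirable to repair and best handled in the same edit. The primary analysis is unaffected.

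**What to change.** In SAP 8.2.9, replace the between-arm signed-rank test at 2 h and at 24 h, in each DB period, with a van Elteren (stratified rank-sum) test that uses the predose functional disability score as the stratum. State in advance how sparse strata, such as score 0, are combined. Within a stratum the predose score is constant, so ranking change or ranking the postdose score gives the same test.

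Van Elteren gives a p-value but no adjusted difference. As the accompanying estimate, report the predose-adjusted mean difference with 95% CI from an ANCOVA of change on treatment and predose score. Keep raw change by arm as a descriptive summary. Record the edit in SAP section 11, because Protocol 11.6.2 also names the signed-rank test.

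The cost is a few sentences in the SAP and minor programming, with no extra data or patients. The downsides are that small strata contribute little and that the ANCOVA estimate treats a four-level score as interval.

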8.2.11. Subject-Rated Treatment Satisfaction at 2 Hours Postdose

The possible values of the subject treatment satisfaction scale are: 1 = very satisfied; 2 = satisfied; 3 = somewhat satisfied; 4 = neither satisfied nor dissatisfied; 5 = somewhat dissatisfied; 6 = dissatisfied; 7 = very dissatisfied.

Subject-rated treatment satisfaction based on a 7-point scale at 2 hours postdose during each DB treatment period will be summarized by treatment group for the FAS1 and FAS2. The corresponding p-values from the Wilcoxon rank-sum test will be computed for the comparison between treatment groups.

The subject-rated treatment satisfaction score at 2 hours postdose and the baseline PPMQ-R response for the same question will be compared for the DFN-02 group only. The corresponding p-value from the Wilcoxon rank-sum test will be computed for this comparison.

The difference between the subject-rated treatment satisfaction score at 2 hours postdose and the baseline PPMQ-R response for the same question will be summarized by treatment group for the FAS1 and FAS2. The corresponding p-values from the Wilcoxon signed-rank test will be computed for the comparison between treatment groups.

Additionally, the subject-rated treatment satisfaction scores will be categorized to report "satisfied" versus "neither/dissatisfied" as well as "satisfied/neither" versus "dissatisfied". The "satisfied" category consists of scores 1-3, and the "neither/dissatisfied" category consists of scores 4-7. The "satisfied/neither" group consists of scores 1-4, and the "dissatisfied" group consists of scores 5-7. Proportions of subjects in the "satisfied" versus "neither/dissatisfied", and the "satisfied/neither" versus "dissatisfied" categories will be summarized by treatment group for the FAS1 and FAS2. The corresponding p-values from Fisher's exact test will be computed for the comparison between treatment groups.

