The change from baseline to 24 hours for each subscale score, each global item score, the total score, and the total raw score will also be analyzed using the Wilcoxon signed-rank test. Baseline scores for each subscale score, each global item score, the total score, and the total raw score will be summarized by treatment group. The total score at 24 hours postdose and the total score at baseline will be compared for the DFN-02 group only. A similar comparison for the total raw scores for the DFN-02 group will be performed. The corresponding p-value from the Wilcoxon rank-sum test will be computed for those two comparisons.

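### The Wilcoxon tests are swapped in several secondary analyses: the paired signed-rank test is assigned between arms, and the independent-samples rank-sum test within the DFN-02 arm

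*SAP*

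**What the plan says.** **Between arms.** SAP 8.2.9 compares change in functional disability at 2 and 24 hours between treatment groups in FAS1 and FAS2: "The corresponding p-values from the Wilcoxon signed-rank test will be computed for the comparison between treatment groups". The fourth paragraph of SAP 8.2.11 uses the same sentence for the difference between the 2-hour satisfaction score and the baseline PPMQ-R item. Protocol 11.6.2 says that the disability change "will be analyzed using Wilcoxon signed-rank test", without saying whether the contrast is between or within arms.

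**Within DFN-02.** In the third paragraph of SAP 8.2.11 the 2-hour satisfaction score and the baseline item "will be compared for the DFN-02 group only. The corresponding p-value from the Wilcoxon rank-sum test will be computed for this comparison". SAP 8.2.12 sets up the same kind of contrast for the PPMQ-R: "The total score at 24 hours postdose and the total score at baseline will be compared for the DFN-02 group only", and likewise for the total raw score. The test is again rank-sum: "The corresponding p-value from the Wilcoxon rank-sum test will be computed for those two comparisons".

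**Elsewhere.** The between-arm comparisons of the 2-hour satisfaction score (8.2.11, second paragraph) and of the 24-hour PPMQ-R scores (8.2.12) correctly use rank-sum. PPMQ-R change from baseline (8.2.12) is given signed-rank with no contrast named. SAP Section 11 repeats the 8.2.11 and 8.2.12 assignments. Neither Note to File changes them.

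**The concern.** The signed-rank test is for one sample of within-subject differences; the rank-sum test is for two independent samples. The plan names each where the other belongs.

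The between-arm half is the serious one. Acute migraine patients tend to improve from their predose state over 2 and 24 hours on placebo too. A signed-rank p-value reflects that shared improvement. If it appears in a table as the comparison of DFN-02 with placebo, it will look like a treatment effect whether or not one exists. Six between-arm p-values are affected: four for disability (2 time points × 2 periods) and two for satisfaction (1 time point × 2 periods).

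Ordinary safeguards may miss this. Under SAP Section 14, quality control is independent programming compared electronically. Two programmers following the same specification would agree on the same wrong test.

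**Working it through.** The plan gives no figure to reproduce. The check sets each test against its contrast, then sizes the consequence.

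**1. Test against contrast**

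| Place | Contrast | Samples | Test named | Test that fits |
|---|---|---|---|---|
| SAP 8.2.9 | disability change, DFN-02 v placebo | different subjects | signed-rank | rank-sum on changes |
| SAP 8.2.11, para 2 | 2 h satisfaction between arms | different subjects | rank-sum | rank-sum |
| SAP 8.2.11, para 3 | 2 h v baseline, DFN-02 only | same subjects | rank-sum | signed-rank |
| SAP 8.2.11, para 4 | difference from baseline between arms | different subjects | signed-rank | rank-sum on differences |
| SAP 8.2.12 | 24 h PPMQ-R scores between arms | different subjects | rank-sum | rank-sum |
| SAP 8.2.12 | PPMQ-R change | not stated | signed-rank | depends on contrast |
| SAP 8.2.12 | total and total raw score, 24 h v baseline, DFN-02 only | same subjects | rank-sum | signed-rank |
| Protocol 11.6.2 | disability change | not stated | signed-rank | rank-sum if between arms |

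Independence of the arms follows from SAP 3.7 (1:1 allocation in each period) and SAP 5.4 (FAS1 analysed by randomized arm, FAS2 by re-randomized arm). Re-randomization lets some subjects receive both treatments, but no DB1-to-DB2 pairing is specified.

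**2. Signed-rank between arms**

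From the documents: 50 per arm (SAP 3.6) and two-sided alpha 0.05 (SAP 6.1.1). Assumed: disability changes of −3, −2, −1, 0, +1 with probabilities 0.05, 0.20, 0.35, 0.30, 0.10 in both arms.

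- Mean change = −0.15 − 0.40 − 0.35 + 0 + 0.10 = −0.80.
- Variance = (0.45 + 0.80 + 0.35 + 0 + 0.10) − 0.80² = 1.70 − 0.64 = 1.06, so SD = 1.03.
- Mean over standard error in one arm = 0.80 / (1.03/√50) ≈ 5.5, far beyond 1.96 with no arm difference at all.

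Rejection rates over 3,000 simulated trials. The alternative gives DFN-02 probabilities 0.15, 0.35, 0.30, 0.15, 0.05, mean −1.4.

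| Procedure | Arms identical | −1.4 v −0.8 |
|---|---|---|
| signed-rank, one arm (DFN-02) | 99.97% | 100% |
| signed-rank, both arms pooled | 100% | 100% |
| signed-rank, arbitrary cross-arm pairs | 4.9% | 79.0% |
| rank-sum on changes | 5.2% | 81.6% |

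The first two rows barely distinguish a treatment effect from none. The third holds its size but needs equal arm sizes and gives no unique answer: over 1,000 re-pairings of one data set p ran from 1.2×10⁻⁶ to 3.8×10⁻⁴, against a single rank-sum value of 8.1×10⁻⁶.

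With 45 per arm and a smaller common improvement of 0.36 to 0.64 points (all assumed), signed-rank rejected in 82% to 99.7% of trials in one arm and 99% to 100% pooled; rank-sum stayed at about 5%.

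**3. Rank-sum within DFN-02**

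With two readings per subject at correlation ρ, the difference in means has variance 2σ²(1−ρ)/n, while an independent-samples test assumes 2σ²/n. True size is then roughly 2[1 − Φ(1.96/√(1−ρ))]:

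- ρ = 0.3: 1.96/0.837 = 2.34, size about 1.9%
- ρ = 0.5: 1.96/0.707 = 2.77, size about 0.6%
- ρ = 0.7: 1.96/0.548 = 3.58, size about 0.04%

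Simulation on 7-point scores (n = 50, 2,000 replicates; assumed latent correlation, and 0.4 SD shift for power):

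| ρ | Rank-sum size | Signed-rank size | Rank-sum power | Signed-rank power |
|---|---|---|---|---|
| 0 | 5.2% | 5.4% | 47% | 46% |
| 0.3 | 1.6% | 3.9% | 48% | 60% |
| 0.5 | 0.9% | 4.5% | 48% | 74% |
| 0.7 | 0.0% | 5.2% | 47% | 92% |

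**The case against.** The strongest reply accepts the wording error and disputes its weight.

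- Only secondary endpoints are touched; the primary analysis is Fisher's exact test (SAP 8.1.1). SAP 6.1.1 presents the study as mainly descriptive. Each domain also has a valid between-arm test: Fisher's test per level of disability change, and rank-sum on the 2-hour satisfaction and 24-hour PPMQ-R scores. **This stands** as a limit on the damage. But Protocol Section 11 commits to hypothesis tests for all secondary endpoints, and a set of per-level Fisher tests does not replace one ordinal comparison of the change.
- The SAP does not say how the signed-rank p-value would be produced. SAP 13.2.4 allows within-treatment p-values beneath each arm's statistics, so a per-arm result might be shown as such, and pooling is nowhere planned. **Partly stands:** the inflation depends on implementation. But 8.2.9 labels the p-value as between groups, and no implementation gives a unique valid one.
- In 8.2.11 the baseline is satisfaction with prior migraine medication, so improvement on placebo cannot be presumed. **Stands.** The shared-improvement argument is for disability. For satisfaction the test still answers the wrong question, and a common shift in either direction would trigger it.
- The within-arm rank-sum test does compare the two time points; it merely ignores the pairing. **Stands.** With positive correlation it is conservative, and at zero correlation nothing is lost.
- Protocol 11.6.2 and the PPMQ-R change sentence name no contrast. **Stands:** they are ambiguous rather than demonstrably wrong.

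**Conclusion.** The concern holds. In SAP 8.2.9 and the fourth paragraph of 8.2.11 the named test cannot make the stated comparison. Applied to one arm or to the pooled arms, with identical arms sharing an improvement of about 0.4 to 0.8 points, it would be significant in roughly 82% to 100% of trials, against about 5% for rank-sum. In the third paragraph of 8.2.11 and in the DFN-02-only comparisons of 8.2.12, the named test is inefficient rather than misleading: at correlation 0.5 its size is 0.9% and its power 48%, where the paired test has 74%.

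The change distributions, correlations, 0.4 SD shift and the 45-per-arm case are assumptions; only 50 per arm and alpha 0.05 come from the documents. The percentages move with those inputs. The mismatch between test and contrast does not, because it follows from the design. The primary endpoint and the existing between-arm rank-sum tests are sound.

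**What to change.** Make these changes before unblinding:

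1. **SAP 8.2.9 and 8.2.11, fourth paragraph:** compare the change scores between arms with the Wilcoxon rank-sum test.
2. **SAP 8.2.11, third paragraph, and the two DFN-02-only comparisons in 8.2.12:** use the Wilcoxon signed-rank test on within-subject differences.
3. **SAP 8.2.12, PPMQ-R change from baseline:** state the contrast. Keep signed-rank if it is within arm; use rank-sum on the changes for any between-arm comparison.
4. **Protocol 11.6.2 and SAP Section 11:** align the protocol sentence on functional disability, or list the departure in Section 11. Correct the repeated 8.2.11 and 8.2.12 text there. The existing 8.2.9 entry covers only the Fisher analysis by level, so the change of test needs a new entry.

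Leave the correct between-arm rank-sum tests as they are. The cost is a few sentences and the matching procedure calls; no data collection, visit or patient is affected. Swapping the tests silently in programming would be an undocumented departure, and doing so after unblinding would look data-driven.
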